8.2.2. Exclusion Criteria

No exclusion criteria will be imposed for the selection of patients.ⁱ

8.3. Variables

For purposes of this study, a regimen will be defined as one or more anti-cancer agents given in combination, over a period of time. Providers will be informed as to the definition of a regimen *but will make the determination themselves as to what constituted a line of therapy in the advanced/metastatic setting*. However, re-assignment of the lines of therapy in the metastatic setting may occur during data analysis based on the dates regimens were initiated and discontinued and the rationale for that discontinuation. For example a patient treated with palbociclib+LET who discontinued palbociclib but continued with LET may be indicated as a single line by the provider but the use of LET monotherapy may be recoded as a subsequent line of therapy during the analysis phase. All dates of initiation and discontinuation of individual agents when received in combination will be abstracted by the patient's treating physician.

Additionally, disease progression is taken to have occurred when a pathology report or radiological scan note indicates disease progression and/or there is a physician progress note consistent with that determination. Providers will be informed of these criteria and indicate the date of disease progression as recorded in the patient charts during initial endocrine therapy for MBC following that guidance.

The table below describes data elements to be abstracted by the provider (“Abstracted Data Points”) and independent/exposure variables calculated from the abstracted data (“Calculated Variables”).

Variable	Operational definition
Patient demographics	Abstracted Data Points: Year of birth, payer, state of residence, ethnicity, weight, height, ER status, PR status, HER2 status, family history of breast cancer. Calculated Variables: age at advanced/metastatic diagnosis, age at initiation of endocrine-based therapy, body mass index.
Clinical characteristics	Abstracted Data Elements: date of initial breast cancer diagnosis, date of diagnosis of advanced/metastatic disease, AJCC stage, node status, menopause status, ECOG-PS (@ treatment for advanced/metastatic disease), sites of metastatic disease (@ initiation of treatment for advanced/metastatic disease), comorbidities (@ initiation of treatment for advanced/metastatic disease). Calculated Variables: time to advanced/metastatic disease, Charlson comorbidity index.

ⁱ Participation in any interventional clinical trials following the diagnosis of metastatic or locoregionally advanced breast cancer will be flagged for further evaluation.

Variable	Operational definition
Neo/adjuvant treatment history	
Abstracted Data Elements: chemotherapy/hormonal therapy regimens received, date of discontinuation of adjuvant treatment, type of surgery, receipt of radiotherapy.
 
Calculated Variables: disease free interval (time from discontinuation of adjuvant therapy to diagnosis of advanced/metastatic disease).

Initial endocrine-based therapy treatment characteristics	
Abstracted Data Elements: Drug and/or combination endocrine partner, date of initiation, date of discontinuation, total number of cycles received, dose at initiation, dose reductions, dose increases, rationale for dose increase/decrease, treatment interruptions (eg, drug holiday), rationale for treatment discontinuation (eg, progression, toxicity, patient choice).
 
Calculated Variables: duration of treatment (DOT) with initial endocrine-based therapy.

Initial endocrine-based therapy laboratory monitoring	
Abstracted Data Elements: Frequency of CBC monitoring, dates of CBC monitoring during first 6 cycles of therapy, dates of cardiac monitoring using electrolyte panel, liver function panel, electrocardiogram.
 
Calculated Variables: None.

Clinical outcomes during initial endocrine-based therapy	
Abstracted Data Elements: provider assessed response to therapy (CR, PR, SD, PD), date of best initial response (CR, PR, SD), date of disease progression, stable disease lasting >24 weeks, favorable/unfavorable response (if stable), development of new measurable target lesions since initiation of endocrine-based therapy.
 
Calculated Variables: visceral disease at initiation of endocrine-based therapy, duration of stable disease, ORR (CR+PR+SD lasting greater than 24 weeks).

Advanced/metastatic treatment patterns following discontinuation of initial endocrine-based therapy	
Abstracted Data Elements: drug regimens received post discontinuation of initial endocrine-based therapy (chemotherapy, switch to alternative endocrine), date of initiation and discontinuation of treatment regimens received.
 
Calculated Variables: total lines of therapy received in the metastatic setting.

Status at last follow-up	
Abstracted Data Elements: date of last follow-up, receipt of hospice care, receipt of palliative care, date of death (if deceased), cause of death.
 
Calculated Variables: None.

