 - c. Treatment patterns includes the distribution of regimens administered, by line, from MBC diagnosis through the end of the medical record.
 - d. Treatment patterns also includes the sequence of treatments across lines, from MBC diagnosis through the end of the medical record.
4. Describe clinical outcomes in terms of objective disease response rates and progression-free survival during treatment:
 - a. Describe the rate of objective disease response during initial endocrine-based therapy:
 - i. Tumor response will be classified per provider report for each regimen received during MBC treatment.
 - ii. Tumor response will be classified under a primary response classification as complete response (CR), partial response (PR), stable disease (SD), progressive disease (PD), and unknown/not evaluated (NE).
 - iii. Tumor response will be classified under a secondary response classification as matching the primary classification, but patients with NE responses classifiable as Other Favorable or Other Unfavorable so classified.
 - b. Describe progression-free survival and/or time to progression from the initiation of initial endocrine-based therapy:
 - i. Landmark PFS and/or rate of progression at 3, 6, 12, 18, and 24 months.
 - ii. Proportion alive at 6, 12 and 24 months.

CCI

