- d. Treatment patterns includes the distribution of regimens administered, by line, from MBC diagnosis through the end of the medical record
- e. Treatment patterns also includes the sequence of treatments across lines, from MBC diagnosis through the end of the medical record

4) Describe the rate of objective disease response during initial endocrine-based therapy

- a. Tumor response will be classified per provider report for each regimen received during MBC treatment
- b. Tumor response will be classified under a primary response classification as complete response (CR), partial response (PR), stable disease (SD), progressive

disease (PD), and not evaluable (NE), and unknown which comprises any other status

- c. Tumor response will be classified under a secondary response classification as matching the primary classification, but for patients with NE, responses classifiable as “Other Favorable” or “Other Unfavorable”

5) Describe PFS from the initiation of initial endocrine-based therapy

- a. Proportion of patients who are persistent to initial endocrine-based therapy for MBC at 3, 6, 12, 18, and 24 months, with persistence defined as the duration of initial regimen until one of the following events occurs: a regimen change or switch, treatment discontinuation, disease progression, or death.
- b. Landmark PFS at 3, 6, 12, 18, and 24 months
- c. Proportion alive at 3, 6, 12, 18 and 24 months

CCI

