1L therapy treatment characteristics	Forms analysis set cohorts, duration of treatment is descriptive outcome	
Abstracted Data Elements: drug and/or combination endocrine partner, date of initiation, date of discontinuation, total number of cycles received, dose at initiation, dose reductions, dose increases, rationale for dose increase/decrease, treatment interruptions (e.g., drug holiday), rationale for treatment discontinuation (e.g., progression, toxicity, patient choice)
 
Calculated Variables: duration of treatment with initial endocrine-based therapy

1L therapy laboratory monitoring	Descriptive outcome	
Abstracted Data Elements: frequency of CBC, cardiac monitoring using electrolyte panel, liver function panel monitoring during first 3 cycles of therapy, date of first CBC, electrolyte panel, ECG, liver function panel
 
Calculated Variables: Time to first test during 1L therapy

Variable	Role/Time Period	Operational definition
Clinical outcomes during initial endocrine-based therapy	Primary clinical outcomes, comparison outcome for palbociclib+LET [REDACTED] CCI	Abstracted Data Elements: provider assessed response to therapy (CR, PR, SD, PD), date of best initial response (CR, PR, SD), date of disease progression, Calculated Variables: duration of stable disease
Advanced/metastatic treatment patterns following discontinuation of initial endocrine-based therapy	Descriptive Outcome	Abstracted Data Elements: drug regimens received post discontinuation of initial endocrine-based therapy (chemotherapy, switch to alternative endocrine), date of initiation and discontinuation of treatment regimens received Calculated Variables: total lines of therapy received in the metastatic setting
Status at last follow-up	Descriptive outcome, death used as part of PFS calculation	Abstracted Data Elements: date of last follow-up, receipt of hospice care, receipt of palliative care, date of death (if deceased), cause of death Calculated Variables: See section 5.1.5

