7 STATISTICAL METHODOLOGY AND STATISTICAL ANALYSES

7.1 DESCRIPTIVE ANALYSIS

All categorical or numeric non time-to-event variables collected from the chart data abstraction or calculated from said data will be analyzed using descriptive statistical techniques. For demographic continuous variables, the mean, standard deviation, median, and minimum/maximum will be calculated as appropriate. For categorical variables, frequencies and percentages will be provided. The number of missing or unknown observations will be described for both categorical and numeric variables. The 95% confidence intervals will be provided as a measure of estimated precision when appropriate. The following characteristics will be described using in each cohort using the statistical techniques previously described: demographics, receipt of and treatment received for neo/adjuvant treatment, clinical characteristics at diagnosis (e.g., stage, nodal status, menopause status), and clinical characteristics at diagnosis of locoregional recurrent or metastatic/initiation of 1L treatment (e.g., comorbidities, ECOG-PS, menopause status, receipt of CBC/cardiac tests in 30 days prior to initiation of 1L). Other descriptive analyses will include assessing the time from diagnosis to the initial initiation of 1L, duration of adjuvant treatment, and duration of follow-up from initiation of 1L treatment.

In addition, during 1L treatment, the following will be described: dose reductions, dose increases, treatment interruptions, and number of palbociclib cycles completed. The following details the assessment of these outcomes. Response levels are those specified in the case report form for the study.

1. Frequency of initiation of 1L palbociclib at 125mg, 100mg, and 75mg
CCI
[REDACTED]
2. Frequency/proportion of patients with any dose reductions and any dose increase
3. Frequency of reported rationale(s) for dose reduction (toxicity, other) and dose increases (no response, suboptimal response, loss of response, disease progression, other)
4. Mean months from initiation of 1L treatment to first dose reduction, first dose increase
5. Frequency of any treatment interruption; mean number of treatment interruptions during 1L treatment
6. Frequency of reported rationale(s) for first treatment interruption (toxicity, no response, loss of response, disease progression, prepare for alternative treatment strategy, patient choice, other)
7. Mean time to first treatment interruption

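### The favorable/unfavorable item is listed for stable-disease patients, but the secondary response classification needs it for not-evaluated (NE) patients

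*Protocol*

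**What the plan says.** **The objective.** Protocol 7.1, objective 4.a, sets a primary response classification of CR, PR, SD, PD and a fifth level; the list ends with "progressive disease (PD), and unknown/not evaluated (NE"). The secondary classification matches the primary one, with "patients with NE responses classifiable as Other Favorable or Other Unfavorable so classified". SAP 2.4, objective 4c, keeps the same plan: "but for patients with NE, responses classifiable as “Other Favorable” or “Other Unfavorable".

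**The data elements.** In the clinical outcomes row of the Protocol 8.3 table, the abstracted elements begin "provider assessed response to therapy (CR, PR, SD, PD), date of best initial response (CR, PR, SD), date of disease progression, stable disease lasting >24". The element after this 24-week one is "favorable/unfavorable response (if stable"). The matching row of SAP Table 2 (section 5.1) is shorter: "provider assessed response to therapy (CR, PR, SD, PD), date of best initial response (CR, PR, SD), date of disease progression". It then goes straight to its one calculated variable, the duration of stable disease, with no favorable/unfavorable item.

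**The analysis.** The disease-response outputs at the end of SAP 7.1 cover whether response was assessed, the CR/PR/SD/PD distribution, objective response, clinical benefit and time to assessment. The secondary classification is not among them.

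**The concern.** The item and the classification it should feed apply to different patients. In the primary classification SD and NE are separate levels, so a patient recorded as SD is not NE. The stated condition therefore asks the question of patients who stay SD under both classifications, and skips the only patients whose label could move.

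At stake is whether one part of a stated objective can be reported. Protocol 8.2 plans data collection over four weeks by the treating physicians. If the question is not put to NE patients then, the answer can be had only by going back to the providers.

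**Working it through.** The documents give no figure to reproduce on this point, so the check is a comparison of the passages, followed by a rough sizing.

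**Step 1. Who is asked, and who needs the answer.**

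| Recorded response | Item asked under Protocol 8.3 | Item listed in SAP Table 2 | Class can change under objective 4.a.iii / 4c |
|---|---|---|---|
| CR or PR | No | No | No |
| SD | Yes | No | No |
| PD | No | No | No |
| NE | No | No | Yes, where classifiable |

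No row has both the item asked and a class that can change. The overlap is zero by construction.

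**Step 2. Is there another route?** I looked for a rule that builds Other Favorable or Other Unfavorable from other fields. Protocol 8.3 and 8.7 and SAP 5.1, 5.4 and 7.1 contain none in the visible text. Neither term is defined.

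**Step 3. Does the SD answer serve another stated purpose?** Clinical benefit (Protocol 8.7, SAP 5.4) uses stable disease lasting more than 24 weeks, which Protocol 8.3 lists as its own element. No named endpoint in the visible text uses a favorable/unfavorable split of SD patients.

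**Step 4. Size.** Inputs are the feasibility counts in Protocol 8.5 and the target of 200 patients.

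- Check of the counts: 126 + 340 + 232 + 95 + 11 = 804, which agrees with the stated total.
- Asked under the stated condition (SD): 232/804 = 28.9%; 0.289 × 200 ≈ 58 patients.
- Need the answer (missing response documentation as a proxy for NE): 11/804 = 1.4%; 200 × 11/804 = 2.7, about 3 patients.
- The NE share in abstracted charts is not given. If it were 5% to 10%, an assumption with no support in the documents, the count would be 10 to 20 of 200.

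**Step 5. What else depends on it.** Objective response is CR + PR. Clinical benefit adds SD beyond 24 weeks. Time to progression and PFS (SAP 7.2) count discontinuation for progression, with death added for PFS. None of these uses the secondary classification.

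**The case against.** The strongest reply is that the tables in Protocol 8.3 and SAP 5.1 summarise data elements and are not the form or its skip logic. SAP 7.1 says "Response levels are those specified in the case report form for the study", and the form is not available, so it may already ask the right question of NE patients. This stands as a limit on the claim. It does not remove the mismatch: that SAP sentence introduces a list of dosing and interruption items, and the only condition the documents state for the item is stable disease.

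Three further arguments limit the point.

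- **NE patients are expected.** A reader might infer from the CR, PR, SD, PD list that the form has no NE level. The documents do not support that. Both sets of objectives name NE, SAP 2.2 provides for unknown or missing options where applicable, and SAP 7.1 counts patients whose response was not evaluable or not available. Only the tables are out of step.
- **Other fields could help.** A reader might infer that the classification cannot be derived at all. Protocol 8.3 also collects the progression date, new measurable target lesions and the reason for discontinuation, without the stable-disease condition. These could inform a favorable or unfavorable call, and the objective covers only NE responses that are classifiable. What is missing is a written rule.
- **The SD answers are not necessarily wasted.** Protocol 8.7 has all collected categorical variables described, so the item would at least be tabulated. Its purpose among SD patients is simply not stated.

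The list in SAP Table 2 also ends on a comma before the calculated variable, so an element may have been lost in editing or text extraction. I read the row as it stands.

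**Conclusion.** The inconsistency is real and of low severity. Protocol 8.3 attaches the favorable/unfavorable item to stable disease, and SAP Table 2 omits it. Protocol objective 4.a.iii and SAP objective 4c use it only for NE patients. From the listed data elements, with no derivation rule, the documents do not show how the secondary classification would be produced. That is as far as they go, because the eCRF is not available.

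The size is about 3 of 200 patients, assuming the feasibility mix carries over and missing response documentation stands in for NE. Both assumptions are loose, since the counts come from a provider query. A reader might also infer that the main response or PFS results are at risk. They are not, because none of them uses this classification. The reason to act is that a stated objective and the data meant to answer it should agree before charts are abstracted.

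**What to change.** Either of two changes brings the objective and the data into agreement.

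1. **Keep the classification.** In Protocol 8.3, SAP Table 2 and the eCRF, ask favorable/unfavorable when the response is NE. Keep the stable-disease question only if a use for it is stated. Show NE and unknown as response levels in both tables, to match the objectives. Define Other Favorable and Other Unfavorable, since moving the condition alone leaves them undefined. Say whether the split covers unknown responses as well: the protocol joins unknown with not evaluated, while the SAP separates unknown from not evaluable. Add the output to the disease-response list in SAP 7.1.
2. **Drop it.** Delete the secondary classification from Protocol 7.1 and SAP 2.4. With so few patients likely to be affected, this is a reasonable choice.

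The first option costs a small branching change on the form and a few lines of text. Protocol 8.6 requires the eCRF and protocol to go back to the IRB for any form change that results from the pre-test, so it is cheaper to settle this before then. The second option needs only text edits and loses a minor descriptive output.

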8.2.1. Inclusion Criteria

Patients must meet all of the following inclusion criteria to be eligible for inclusion in the study:

1. Diagnosed with locoregional recurrent or metastatic female breast cancer.
2. Pathologically confirmed HR-positive/HER2-negative diagnosis.
3. Received treatment with palbociclib in combination with letrozole as initial endocrine-based therapy for advanced/metastatic breast cancer:
 - a. Initiated treatment with palbociclib at least 3 months following the provider's first use of palbociclib following its FDA approval.
 - b. At least 1 month of follow-up (at least one visit with the provider) after initiation of palbociclib.
4. Postmenopausal (or receiving surgical or medical treatment to induce menopause) at the time of initiation of palbociclib.
5. ≥ 18 year old at initiation of palbociclib.

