2 STUDY DESIGN

Patient demographics, clinical characteristics, treatment patterns pre- and post-palbociclib, laboratory monitoring, dosing patterns (and rationale for dosing changes), and clinical outcomes, including disease response and PFS will be described for locoregional recurrent or metastatic patients receiving palbociclib+LET as 1L, [REDACTED]

[REDACTED] The data will be collected through a physician-led, retrospective chart review. Providers will identify patients meeting the study selection criteria and abstract data from his/her patients' medical records into an electronic case report form (eCRF). Cardinal Health will conduct data verification via telephone and electronic follow-up. [REDACTED]

CCI

[REDACTED]

- 1) Presence of visceral metastases at the initiation of initial endocrine therapy for MBC
- 2) Receipt of prior neo/adjuvant endocrine therapy
- 3) De novo metastatic disease, ≤ 12 months disease free interval since prior neo/adjuvant treatment, >12 months disease free interval since prior neo/adjuvant treatment

CCI

[REDACTED]

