2.1 STUDY POPULATION

CCI

[REDACTED]

- 1) Patients treated with palbociclib+LET as initial endocrine therapy for MBC per the palbociclib U.S. FDA approval label;

CCI

[REDACTED]

The target sample size for each of the three cohorts is 200 patients. Table 1 illustrates the selection criteria for each of the cohorts. Patients must meet all of the following inclusion criteria to be eligible for inclusion in the study. No exclusion criteria will be imposed for the selection of patients.

Table 1. Cohort Selection Criteria.

Palbociclib+LET	CCI
Diagnosed with locoregional recurrent or metastatic female breast cancer	
Pathologically confirmed HR-positive/HER2-negative tumor	
Received treatment with palbociclib in combination with LET as initial endocrine-based therapy for advanced/metastatic breast cancer 
 - Initiated treatment with palbociclib at least 3 months following the provider's first use of palbociclib after 03 Feb 2015 - At least 1 month of follow-up data after initiation of palbociclib 	
Postmenopausal (or receiving surgical or medical treatment to induce menopause) at the time of initiation of 1L treatment for locoregional recurrent or BMC	
≥18 year old at initiation of endocrine therapy	

Patient eligibility will be confirmed by the treating physician. Providers may complete a maximum of 20 eCRFs. Providers will be asked to randomly select patients from the pool of eligible patients and verify that they have performed random patient selection.

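### Neither data-element table lists systemic therapy given between MBC diagnosis and palbociclib+LET, so line counts and sequences would be wrong for any chemotherapy-first patient enrolled

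*Protocol*

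**What the plan says.** **Eligibility.** Protocol 8.2.1, item 3: "Received treatment with palbociclib in combination with letrozole as initial endocrine-based therapy for advanced/metastatic breast cancer". SAP Table 1 (section 2.1) matches it: "Received treatment with palbociclib in combination with LET as initial endocrine-based therapy for advanced/metastatic breast cancer". Protocol 8.2.2 adds: "No exclusion criteria will be imposed for the selection of patients"; SAP 2.1 says the same.

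**Objectives.** Protocol 7.1, 3c: "Treatment patterns includes the distribution of regimens administered, by line, from MBC diagnosis through the end of the medical record". Protocol 7.1, 3d: "Treatment patterns also includes the sequence of treatments across lines, from MBC diagnosis through the end of the medical record". SAP 2.4 repeats both as items 3d and 3e.

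**Data elements.** Protocol 8.3 and SAP Table 2 list anticancer drugs in three places: neo/adjuvant history, the initial endocrine-based (in the SAP, 1L) regimen, and "drug regimens received post discontinuation of initial endocrine-based therapy (chemotherapy, switch to alternative endocrine"). The last row carries the calculated variable "total lines of therapy received in the metastatic setting".

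**Line definition and cohort label.** SAP 2.3 defines first line as the first regimen begun after locoregional recurrent or metastatic diagnosis, with neo/adjuvant regimens not counted. SAP sections 2, 3 and 5 call the palbociclib+LET cohort 1L. SAP 2 also says the study will describe "treatment patterns pre- and post-palbociclib".

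**The concern.** The inclusion criteria turn on the first endocrine-based therapy, while the SAP's line numbering turns on the first therapy of any kind. The two coincide only if nobody received chemotherapy for MBC before palbociclib+LET. Neither inclusion list requires that, and no listed data element would show whether it is true.

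At stake are the descriptive treatment-pattern outputs: regimens by line, sequence across lines, total lines, the second-line regimen distribution (SAP 7.1, item 12), and the time from diagnosis to start of 1L (SAP 7.1). Each starts from MBC diagnosis or depends on correct line numbers.

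**Working it through.** The plan states no figure on this point to reproduce. The check sets the sections side by side; the arithmetic at the end is illustrative.

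**1. Who can enter.** Protocol 8.2.1 and SAP Table 1 need palbociclib+LET as the first endocrine-based therapy, and no exclusions apply. Read literally, a woman given chemotherapy for MBC and then palbociclib+LET qualifies. Under SAP 2.3 her palbociclib+LET is second line. Under the SAP's cohort label it is 1L.

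**2. Which intervals are listed.**

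| Interval | Drug regimens listed (Protocol 8.3; SAP Table 2)? |
|---|---|
| Neo/adjuvant | Yes |
| MBC diagnosis to start of palbociclib+LET | No |
| Palbociclib+LET | Yes |
| After its discontinuation | Yes |

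The four periods in SAP 5 have no place for the second row either.

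**3. Which outputs need the missing interval.** Objectives 3c and 3d, and total metastatic lines. Response is also to be classified for each regimen given during MBC treatment (Protocol 7.1, objective 4a; SAP 2.4, item 4a).

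**4. Can analysis repair it?** Protocol 8.3 allows lines to be re-assigned from regimen dates and reasons for stopping. That can split or relabel recorded regimens. It cannot recover one that was never recorded.

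**5. One patient followed through.** Chemotherapy for MBC, then palbociclib+LET, then regimen B.

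| | Under SAP 2.3 | From the listed elements |
|---|---|---|
| Chemotherapy | Line 1 | Absent |
| Palbociclib+LET | Line 2 | Line 1 |
| Regimen B | Line 3 | Line 2 (enters SAP 7.1, item 12) |
| Total lines | 3 | 2 |

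Her time from diagnosis to 1L would also include the chemotherapy period.

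**6. Size.** Inputs: N = 200 (target in the Protocol abstract and SAP 2.1); f = share of chemotherapy-first patients, an assumption because the documents do not give it; one unlisted regimen each, the minimum for such a patient.

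- Patients affected = N × f
- Shortfall in mean total lines = f × 1
- True share with palbociclib+LET as line 1 = 1 − f (it would be tabulated as 100%)

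| f (assumed) | Patients affected | Mean total lines low by | True line-1 share |
|---|---|---|---|
| 0% | 0 | 0 | 100% |
| 1% | 2 | 0.01 | 99% |
| 5% | 10 | 0.05 | 95% |
| 10% | 20 | 0.10 | 90% |
| 20% | 40 | 0.20 | 80% |

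At f = 1%, the chance of at least one such patient among 200, treating patients as independent, is 1 − 0.99^200 = 0.87. More than one unlisted regimen per patient would enlarge the shortfall in proportion.

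**The case against.** The strongest reply is that chemotherapy-first patients were never meant to enter. SAP 2.3 defines first line as the first regimen after diagnosis, and the SAP then calls the cohort 1L throughout. SAP Table 1 anchors menopausal status at start of 1L where Protocol 8.2.1 anchors it at start of palbociclib, as if the two were the same moment. Protocol 8.6 has date checks on first-line initiation, and SAP 4 describes an eligibility questionnaire with programmatic checks. If that was the intent, the missing interval is empty and the outputs are correct. This has weight: the share may be zero, and it would be wrong to say that the outputs will be in error. But neither inclusion list states the restriction, so the documents conflict and one of them needs to change.

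Four stronger readings are tempting, and the documents do not support them:

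- *The data will not be collected.* The eCRF is not among the documents. What can be said is that neither table lists the element, although both tables are presented as describing what providers abstract.
- *These patients cannot be identified.* The dates of MBC diagnosis and of treatment start are both abstracted, so a long gap would show and could be queried under Protocol 8.8 or SAP 6. The gap alone would not say whether treatment or delay filled it.
- *The SAP breaks its promise of* "treatment patterns pre- and post-palbociclib". Neo/adjuvant therapy is treatment before palbociclib, and it is listed. The point rests on objectives 3c and 3d and on total lines, not on this phrase.
- *ORR, CBR and PFS are invalid.* They are assessed during, or measured from the start of, palbociclib+LET and remain calculable.

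**Conclusion.** The point holds as a conflict between the eligibility wording and the line definition, together with a gap in the listed data elements. For each enrolled patient who had chemotherapy for MBC before palbociclib+LET, that regimen would appear as line 1, total lines would be at least 1 too low, later regimens would be numbered at least one line too early, and time to 1L would be overstated by the chemotherapy period.

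The overall size is unknown. Across an assumed share of 0% to 20%, with one unlisted regimen each, it runs from no effect to 40 of 200 patients and a mean total-lines shortfall of 0.20. The conclusion assumes that abstraction follows the two tables as written. The effect is confined to the treatment-pattern descriptions. It is worth correcting because, if the true share is zero, the listed elements give no direct way to show it.

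**What to change.** 1. Add one conditional element to Protocol 8.3 and SAP Table 2: any systemic therapy after locoregional recurrent or metastatic diagnosis and before palbociclib+LET (yes/no; if yes, drugs with start and stop dates).
2. Reconcile the first-endocrine-therapy wording in the inclusion criteria with the 1L label and SAP 2.3. The sponsor should state which population is meant:
   - If such patients are eligible, count these regimens in the line numbers and in total lines, and report how many patients there are. A sensitivity table of outcomes without them is optional.
   - If they are not eligible, say so in both inclusion lists and use the yes/no item as a screen.

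The cost is one short extra eCRF item, with follow-up fields only for patients answering yes, and matching text in the two documents. It is cheap before data collection; afterwards it would mean returning to the providers.
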